13.0 Statistical Considerations

13.1. Study Design/Endpoints

The primary objective will be measured by the primary endpoint of Objective Response Rate (per RECIST 1.1) among all treated subjects. Secondary endpoints include PFS (per RECIST 1.1) and OS. As discussed in the background, no second line treatments have been studied prospectively for high grade neuroendocrine carcinomas and small retrospective studies have shown dismal results with chemotherapy[11-13]. Hence we decided to proceed with a single stage statistical design given minimal if any, harm associated with ineffective therapy to study participants.

A proportion of patients with favorable response less than 5.0% will be of no interest. The investigational agent would be of interest if the ORR is at least 20.0%. Estimates are based on historical controls from published data {Hentic, 2012 #70;Olsen, 2012 #71;{Sorbye, 2013 #36}. Only those patients who have measurable disease present at baseline, have received at least one cycle of therapy, and have had their disease re-evaluated will be considered evaluable for response. (Note: Patients who exhibit objective disease progression prior to the end of cycle 1 will also be considered evaluable.) Patients who are not evaluable for response will be replaced. However, all patients who received at least 1 dose of the study drug will be included in the safety analysis. Twenty-one patients would be needed to test the null hypothesis: $p \le 0.05$ against the alternative hypothesis: $p \ge 0.20$ at the 8.5% level of significance and with 82.1% power. After 21 patients are evaluated if 3 or more patients with favorable response are observed then the null hypothesis is rejected.

Early stopping rules for safety/adverse events:

Adverse events will be assessed continuously throughout the study. If 6 of the first 12 patients have to discontinue study treatment due to treatment related adverse events the study will be interrupted for consideration of dose reduction or termination. If ever 8 of the 21 eligible patients have to discontinue study treatment due to treatment related adverse events the study will be suspended and early termination for excess toxicity will be considered after careful investigation of the causes of the higher than expected toxicities. Once the root of the higher than anticipated toxicities has been determined, the study team will confer with the FCCC DSMC and IRB to make a determination whether accrual can be resumed or the study will be terminated early. The chance of early termination with a true toxicity of 50% is 61%. The chance of study termination under the null of 20% true toxicity is 2.7% and is 83% if true toxicity is 50%.

As discussed earlier, no second line therapies have been prospectively evaluated in high grade neuroendocrine carcinomas and small retrospective studies have shown dismal results with chemotherapy [11-13]. Hence we decided to proceed without a definite stopping rule for futility, given minimal if any, harm associated with ineffective therapy to study participants.]

Correlative studies: Due to this limited sample size, all exploratory analyses of associations of biomarkers with outcomes and changes in marker levels pre- and during treatment will be largely descriptive in nature.

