8.1.6. Prior Treatment Details

The investigator or qualified designee will review all prior cancer treatments including systemic treatments, radiation and surgeries.

Subsequent Anti-Cancer Therapy Status

The investigator or qualified designee will review all new anti-neoplastic therapy initiated after the last dose of trial treatment. If a subject initiates a new anti-cancer therapy within 30 days after the last dose of trial treatment, the 30 day Safety Follow-up visit must occur before the first dose of the new therapy. Once new anti-cancer therapy has been initiated the subject will move into survival follow-up.

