12.1. Definitions

Evaluable for adverse events. All patients will be evaluable for adverse events from the time of their first treatment with pembrolizumab.

Evaluable for objective response. Only those patients who have measurable disease present at baseline, have received at least one cycle of therapy, and have had their disease reevaluated will be considered evaluable for response. These patients will have their response classified according to the definitions stated below. (Note: Patients who exhibit objective disease progression prior to the end of cycle 1 will also be considered evaluable.)

Evaluable Non-Target Disease Response. Patients who have lesions present at baseline that are evaluable but do not meet the definitions of measurable disease, have received at least one cycle of therapy, and have had their disease re-evaluated will be considered evaluable for non-target disease. The response assessment is based on the presence, absence, or unequivocal progression of the lesions.

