13.2. Sample Size/Accrual Rate

We plan to accrue 21 eligible patients. The expected monthly accrual rate is 1-2 patients. Thus, accrual is anticipated to take approximately 2 years.

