13.4. Reporting and Exclusions

- 13.4.1 Evaluation of toxicity: All patients will be evaluable for toxicity from the time of their first treatment with pembrolizumab
- 13.4.2 Evaluation of response: All patients included in the study must be assessed for response to treatment, even if there are major protocol treatment deviations or if they are ineligible. Each patient will be assigned one of the following categories: 1) complete response, 2) partial response, 3) stable disease, 4) progressive disease, 5) early death from malignant disease, 6) early death from toxicity, 7) early death because of other cause, or 9) unknown (not assessable, insufficient data). [Note: By arbitrary convention, category 9 usually designates the "unknown" status of any type of data in a clinical database.]

All of the patients who met the eligibility criteria (with the possible exception of those who received no study medication) should be included in the main analysis of the response rate. Patients in response categories 4-9 should be considered to have a treatment failure (disease progression). Thus, an incorrect treatment schedule or drug administration does not result in exclusion from the analysis of the response rate. Precise definitions for categories 4-9 will be protocol specific.

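### Sections 12.1/13.1 and 13.4.2 set conflicting denominators for the primary ORR, and the 13.1 replacement rule can overstate ORR and raise type I error

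*Combined protocol and SAP*

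**What the plan says.** Three statements bear on who is counted in the primary analysis.

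- **All treated.** Section 13.1 opens: "The primary objective will be measured by the primary endpoint of Objective Response Rate (per RECIST 1.1) among all treated subjects".
- **Evaluable, with replacement.** Section 13.1 then repeats the Section 12.1 definition: patients with measurable disease at baseline who "have received at least one cycle of therapy, and have had their disease reevaluated will be considered evaluable for response". Objective progression before the end of cycle 1 also makes a patient evaluable. It continues: "Patients who are not evaluable for response will be replaced". The decision rule uses the same set: "After 21 patients are evaluated if 3 or more patients with favorable response are observed then the null hypothesis is rejected".
- **All eligible, failures included.** Section 13.4.2 says that patients who met the eligibility criteria, possibly except those never dosed, "should be included in the main analysis of the response rate". Categories 4 to 9, which include early death from any cause and unknown or not assessable, count as treatment failures.

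Section 12.5 refers only to a proportion of subjects. Section 13.2 says "We plan to accrue 21 eligible patients" and gives no number for replacements; the trial summary (Section 1.0) also gives 21. No section ranks these rules.

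**The concern.** A treated patient who leaves before any re-assessment, without documented objective progression, is a failure under 13.4.2 but is removed and replaced under 13.1. The first on-treatment scan is due at week 9 (Section 8.2.5), and Section 4.1 describes an aggressive disease, so some such losses are plausible. The routes are death, clinical decline, withdrawal, loss to follow-up, or new therapy before the first scan. On new therapy, Section 8.1.6 says: "Once new anti-cancer therapy has been initiated the subject will move into survival follow-up".

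These patients are probably non-responders, so removing them pushes ORR upwards. Replacing them also gives the trial further chances to reach three responders. The trial is single-arm and open-label, response is determined by the investigator, and the conclusion turns on three responders. An unsettled denominator could therefore be chosen after the responses are known.

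**Working it through.** **Inputs.** From Section 13.1: null rate 5%, alternative 20%, 21 evaluated patients, reject at 3 or more responders, stated alpha 8.5% and power 82.1%. From Section 13.2: target 21. Assumed, because the documents do not give it: a share q of treated patients is non-evaluable, with q = 5, 10, 15 or 20%, and all of them are non-responders.

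**1. The plan's own figures.** Exact binomial, X ~ Bin(21, p):

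- Alpha: P(X ≥ 3 | p = 0.05) = 1 − (0.3406 + 0.3764 + 0.1981) = 0.0849, which matches 8.5%.
- Power: P(X ≥ 3 | p = 0.20) = 1 − (0.0092 + 0.0484 + 0.1211) = 0.8213, which matches 82.1%.

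**2. Replacement followed, rates referring to all treated patients.** If the all-treated response rate is p, the rate among evaluable patients is p/(1 − q). Reaching 21 evaluated patients takes on average 21/(1 − q) treated. Type I error is P(X ≥ 3 | 21, 0.05/(1 − q)).

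| q | Expected treated | 5% reads as | Type I error | 20% reads as |
|---|---|---|---|---|
| 5% | 22.1 | 5.3% | 9.6% | 21.1% |
| 10% | 23.3 | 5.6% | 10.8% | 22.2% |
| 15% | 24.7 | 5.9% | 12.3% | 23.5% |
| 20% | 26.3 | 6.25% | 14.0% | 25.0% |

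Type I error passes 10% at q = 6.8%.

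**3. Effect on the estimate.** Take three responders and 1 to 5 replaced patients. Section 13.1 gives 3/21 = 14.3%. Section 13.4.2 gives 3/22 = 13.6% down to 3/26 = 11.5%.

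**4. No replacement: the first 21 dosed patients, non-evaluable counted as failures.** If 5% and 20% refer to this set, step 1 applies unchanged: 8.5% and 82.1%. If they were meant for evaluable patients, the rates on this set become 0.05(1 − q) and 0.20(1 − q):

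| q | Alpha | Power |
|---|---|---|
| 5% | 7.5% | 79.1% |
| 10% | 6.6% | 75.6% |
| 15% | 5.8% | 71.8% |
| 20% | 5.0% | 67.6% |

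**The case against.** The strongest reply is that the evaluability definition, the replacement rule and 3-of-21 form one coherent test on evaluable patients, with alpha exactly 0.0849. Inflation arises only if the 5% null refers to all treated patients. Section 13.1 takes its rates from published historical controls, whose denominators the documents do not give. This stands as a condition on the type I error claim. It does not remove the conflict, because the same section states the endpoint in all treated subjects.

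The inflation also comes from continued accrual, not from the choice of denominator. Once 21 patients have been evaluated, the responder count and the decision are the same under either denominator, and only the percentage differs. That is correct. But whether accrual continues past 21 treated patients is itself what 13.1 and 13.4.2, read with 13.2, leave open.

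The group at issue is narrow. Early objective progressors stay in. Patients who stop without progression continue to be imaged (Section 8.5.3 and footnote l of the calendar in 10.1). Section 12.4 asks for objective documentation after symptomatic deterioration. Only patients never re-assessed are lost, so the lower end of the assumed range may be the realistic one. At q = 5% alpha rises by about one point, and the shift in the estimate is small beside the exact 95% interval for 3/21, which is 3.0% to 36.3%.

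Section 13.2 expects 1 to 2 patients a month for about 2 years, that is 24 to 48, so there is probably room for replacements. The stated target is still 21.

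Finally, 13.4.2 reads like general template text, and a sentence of precedence would resolve the conflict. No such sentence exists, and 13.4.2 calls its own analysis the main one.

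**Conclusion.** The point holds and must be fixed: the primary endpoint has contradictory analysis sets, within 13.1 and between 12.1/13.1 and 13.4.2. That conclusion rests on the text alone.

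The size rests on assumptions. With 5% to 20% of treated patients non-evaluable, all non-responders, and the null on all treated patients, type I error under replacement is 9.6% to 14.0% against the stated 8.5%. If the null was meant for evaluable patients, alpha stays at 8.5%. On either reading, once a non-responder has been replaced the 13.1 estimate is higher than the all-treated rate.

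**What to change.** Define one primary set, for example the first 21 eligible patients who receive at least one dose. Count anyone without a qualifying CR or PR, including patients never re-imaged, as a non-responder. Delete replacement for the primary test and keep 3-of-21 on that set. State that the 5% and 20% rates refer to it. State whether a treated patient later found ineligible counts: the all-treated wording in 13.1 includes such a patient, while the main analysis in 13.4.2 does not. Report the response-evaluable ORR as a sensitivity analysis. Align 12.1, 13.1, 13.2 and 13.4.2, and settle the set before response data are analysed.

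The cost is protocol wording and a slightly less favourable ORR, with no extra patients. If 5% and 20% refer to the new set, the stated alpha and power hold. If they were meant for evaluable patients, the rule becomes conservative, as in step 4 of the working, and the plan should say so. In that case, regaining at least the stated power with the cutoff kept at 3 would take 23, 24, 25 or 27 dosed patients at q = 5, 10, 15 or 20%, with alpha between 8.8% and 9.4%.

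### The toxicity rule as written does not have its stated 2.7% and 83% probabilities, and uncapped replacement of patients moves it further away

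*Combined protocol and SAP*

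**What the plan says.** All of the rule is in Section 13.1, under the early stopping rules for safety.

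- First look: "If 6 of the first 12 patients have to discontinue study treatment due to treatment related adverse events", the study is interrupted so that dose reduction or termination can be considered.
- Second look: "If ever 8 of the 21 eligible patients" discontinue for the same reason, then "the study will be suspended and early termination for excess toxicity will be considered". The data safety monitoring committee and the IRB are consulted on whether accrual resumes.
- Stated performance: 61% for early termination at a true 50% rate, and then "The chance of study termination under the null of 20% true toxicity is 2.7% and is 83% if true toxicity is 50" per cent.

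The same section says, for the response endpoint, "Patients who are not evaluable for response will be replaced". It sets no maximum number of replacements, and the efficacy test needs 21 evaluated patients. The next sentence says that "all patients who received at least 1 dose of the study drug will be included in the safety analysis". Sections 12.1 and 13.4.1 also make all patients evaluable for toxicity from their first treatment. Section 13.2 plans 21 eligible patients.

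**The concern.** There are two linked problems. First, the stated probabilities should follow from the limits by simple binomial arithmetic, and two of the three do not. Either the limit or the figures are wrong, and a committee that relies on the text cannot tell which.

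Second, the rule is written for a fixed group of 21, but replacement means that more than 21 eligible patients can be treated. The text does not say whether the 21 are the first 21 treated or whether the count of 8 runs over everyone treated. If it runs over everyone, each extra patient raises the chance of reaching 8 when the true rate is tolerable. If it covers only the first 21, later patients fall outside any numerical limit.

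This is the trial's only prespecified numerical stopping boundary, because Section 13.1 sets no futility rule. Its properties should be known and correctly stated.

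**Working it through.** **Inputs, all from Section 13.1.** Limits: 6 of the first 12, and 8 of 21. True rates: 20% and 50%. Stated results: 61%, 2.7% and 83%. The number of replacements is not given; 1 to 4 (22 to 25 treated) is assumed below.

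**Formula.** Let X₁₂ be the number of discontinuations in the first 12 patients, N the total counted, r the second limit and p the true rate.

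P(trigger) = P(X₁₂ ≥ 6) + Σ (x = 0 to 5) P(X₁₂ = x) × P(Bin(N − 12, p) ≥ r − x)

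Continuous checking of the second limit adds nothing, because the cumulative count never falls.

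**Step 1: the plan's first figure.** P(Bin(12, 0.5) ≥ 6) = 61.3%. This reproduces the stated 61%. At a true 20% rate the first look triggers with probability 1.94%.

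**Step 2: the whole rule as written, r = 8, N = 21.**

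- At 20%: 1.94% from the first look + 3.09% from the second = 5.0%. Stated: 2.7%.
- At 50%: 61.28% + 29.74% = 91.0%. Stated: 83%.

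The second limit taken alone (8 of 21, no first look) gives 4.3% and 90.5%, which does not match either.

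**Step 3: which limit do the stated figures belong to?** With r = 9, N = 21:

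- At 20%: 1.94% + 0.80% = 2.74%.
- At 50%: 61.28% + 21.98% = 83.3%.

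Both stated figures are reproduced. Alternatives with a first limit of 5 or 7, or with N of 20 or 22, do not reproduce the pair. The pattern is what one would see if the probabilities were computed for more than 8 and the text written as 8, although the documents do not say so.

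**Step 4: more than 21 patients counted.** Same formula, with N raised and the limits unchanged:

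| Patients counted | Limit 8: 20% rate | Limit 8: 50% rate | Limit 9: 20% rate | Limit 9: 50% rate |
|---|---|---|---|---|
| 21 | 5.0% | 91.0% | 2.7% | 83.3% |
| 22 | 6.2% | 93.6% | 3.2% | 87.1% |
| 23 | 7.7% | 95.5% | 3.8% | 90.4% |
| 24 | 9.4% | 96.9% | 4.6% | 92.9% |
| 25 | 11.3% | 97.9% | 5.5% | 94.9% |

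The limit-9 columns show only that the stated figures, even with the limit they match, hold for exactly 21 patients. They are not a proposal.

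**The case against.** The strongest reply is that little turns on this. Reaching a limit leads to interruption or suspension, an investigation and a decision with the committee and the IRB, not to automatic termination. The written limit of 8 is also more likely to trigger at both rates than the figures claim, so patients are not less protected than stated. The size of the inflation beyond 21 depends on a replacement count that the documents do not give. If the rule is applied to the first 21 eligible treated patients, there is no inflation; later patients would still be covered by continuous adverse event assessment (13.1), review of serious events as they occur (14.1) and possible committee review (14.2).

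Much of this stands. The outcome is properly a suspension for review, the larger values are conditional on the assumed replacements, and the first-21 reading is available. But that reading is not stated, and it leaves later patients without a numerical limit. None of the reply explains why the stated probabilities fail with exactly 21 patients and no replacement.

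A reader might also infer something stronger: that patients who stop for toxicity before their first scan are not evaluable for response, are replaced, and so drop out of the toxicity count. The documents do not support this.

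- The second limit refers to eligible patients, not evaluable ones. A patient who stops for toxicity remains eligible.
- Sections 12.1, 13.1 and 13.4.1 keep every dosed patient in the safety evaluation.
- Imaging continues after discontinuation without progression (Section 8.5.3 and the imaging footnote to the calendar in 10.1), so many early withdrawals could still become evaluable.
- The first look counts the first 12 patients without qualification, and alone triggers with probability 61.3% at a true 50% rate.

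**Conclusion.** The point holds in two parts.

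The firm part needs no assumption beyond independent patients with a common rate. For the rule as written with 21 patients, the trigger probabilities are 5.0% and 91.0%, not 2.7% and 83%. The false-suspension probability at a true 20% rate is therefore nearly twice the stated value (5.03 / 2.74 = 1.8), and the probability at a true 50% rate is about 8 percentage points higher than stated. The stated pair matches a limit of 9 of 21. The documents do not show whether the limit or the figures contain the slip.

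The conditional part is that, if the fixed count of 8 runs over all treated patients, the false-suspension probability at a true 20% rate rises to 6.2% with one replacement, 7.7% with two and 11.3% with four. These numbers of replacements are assumed. Under a first-21 reading the 5.0% stands, but patients treated after the 21st have no limit. The text does not choose between the two readings.

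The finding does not extend to a claim that early toxicity withdrawals are left uncounted.

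**What to change.** Amend Section 13.1 as follows.

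1. Reconcile the written second limit with its stated probabilities. Which limit applies is for the sponsor to decide.
2. State that both looks count all patients who received at least one dose, in order of first dose, whether or not they are later replaced for the response endpoint. This is the safety population that Sections 13.1 and 13.4.1 already use.
3. Say what applies to patients treated beyond the 21st.
4. Restate the probabilities for the resulting rule, over the range of treated numbers that the sponsor considers plausible, and describe them as probabilities of suspension for review.

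The cost is a few sentences and a short exact calculation. Neither sample size nor the efficacy test changes. The correction to the figures is not trivial: if the limit of 8 is kept, even with no replacement, 2.7% becomes 5.0% and 83% becomes 91.0%.

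### The toxicity stopping rule as written (6 of the first 12, or 8 of 21) trips with probability 5.0% at 20% toxicity and 91.0% at 50%, not the stated 2.7% and 83%

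*Combined protocol and SAP*

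**What the plan says.** The rule is in section 13.1 under the heading on early stopping for safety and adverse events. It has two limbs, both counting discontinuations for treatment-related adverse events.

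- First limb: "If 6 of the first 12 patients have to discontinue study treatment due to treatment related adverse events the study will be interrupted", with dose reduction or termination then to be considered.
- Second limb: "If ever 8 of the 21 eligible patients have to discontinue study treatment due to treatment related adverse events the study will be suspended", after which "early termination for excess toxicity will be considered after careful investigation of the causes".

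Monitoring is ongoing: "Adverse events will be assessed continuously throughout the study". The planned number in section 13.2 is also 21: "We plan to accrue 21 eligible patients".

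Three probabilities follow the rule. The first is "The chance of early termination with a true toxicity of 50% is 61"%. The other two are in one sentence: "The chance of study termination under the null of 20% true toxicity is 2.7% and is 83% if true toxicity is 50"%. No other section gives a different toxicity limit.

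**The concern.** The 2.7% and 83% are presented as the properties of the rule just stated. If they belong to a different rule, then either the limit or its probabilities are wrong, and the text does not show which. This is the only numerical safety stopping rule in a single-arm trial that has no futility rule. The IRB and the data and safety monitoring committee would be judging its false-alarm rate and sensitivity from figures that do not describe it. If the figures reflect the intended design, the limit the sites act on is misstated by one event.

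**Working it through.** **Inputs, all from section 13.1.** First limb: 6 or more of the first 12. Second limb: 8 or more of 21. True toxicity *p* = 0.20 and 0.50. Stated results: 61% (at 0.50), and 2.7% and 83%.

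**Model.** Patients are independent, each discontinues for a treatment-related event with probability *p*, and every discontinuation is known when a limit is checked. Write X12 for the count in the first 12 patients and X9 for the count in the next 9.

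**Step 1: the figure that reproduces.** P(X12 ≥ 6) at *p* = 0.50 is 0.6128, the stated 61%. This shows that 6 of 12 means 6 or more and that exact binomials were used. At *p* = 0.20 the same probability is 0.0194.

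**Step 2: the written rule.** With second limit *r*,

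P(trip) = P(X12 ≥ 6) + Σ over x = 0..5 of P(X12 = x) × P(X9 ≥ r − x).

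For *r* = 8 the terms of the sum are:

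| x | *p* = 0.20: P(X12 = x) × P(X9 ≥ 8 − x) | *p* = 0.50: P(X12 = x) × P(X9 ≥ 8 − x) |
|---|---|---|
| 0 and 1 together | 0.0001 | 0.0003 |
| 2 | 0.2835 × 0.0031 = 0.0009 | 0.0161 × 0.2539 = 0.0041 |
| 3 | 0.2362 × 0.0196 = 0.0046 | 0.0537 × 0.5000 = 0.0269 |
| 4 | 0.1329 × 0.0856 = 0.0114 | 0.1208 × 0.7461 = 0.0902 |
| 5 | 0.0532 × 0.2618 = 0.0139 | 0.1934 × 0.9102 = 0.1760 |
| Sum | 0.0309 | 0.2974 |

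- *p* = 0.20: 0.0194 + 0.0309 = **0.0503**, against 2.7% stated.
- *p* = 0.50: 0.6128 + 0.2974 = **0.9102**, against 83% stated.

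A patient-by-patient recursion with continuous checking gives the same two values.

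**Step 3: other readings that keep the limit at 8.**

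| Reading | *p* = 0.20 | *p* = 0.50 |
|---|---|---|
| 8 of 21 alone | 4.31% | 90.54% |
| 8 of 21, only after passing the first limb | 3.09% | 29.74% |
| 6 of 12, or 8 of 18 | 2.73% | 78.74% |
| 6 of 12, or 8 of 19 | 3.29% | 83.60% |
| 6 of 12, or 8 of 20 | 4.05% | 87.71% |
| 6 of 12, or 8 of 22 | 6.23% | 93.57% |
| 6 of 12, or 8 of 23 | 7.68% | 95.48% |

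None gives the stated pair.

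**Step 4: the rule that does reproduce it.** With *r* = 9:

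- *p* = 0.20: 0.0194 + 0.0080 = 0.0274, the stated 2.7%.
- *p* = 0.50: 0.6128 + 0.2198 = 0.8326, the stated 83%.

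With 6 of 12 fixed, a search over totals of 13 to 30 patients and second limits of 6 to 13 finds only 9 of 21 matching both figures. A second search, over all two-limb rules with 21 patients and a first look after 5 to 20 of them, finds only 6 of 12 with 9 of 21.

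**Step 5: where the two limits lead to different action.** They differ only when X12 < 6 and exactly 8 of the 21 discontinue.

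| True toxicity | Trip, 8 of 21 | Trip, 9 of 21 | Probability of differing |
|---|---|---|---|
| 20% | 5.0% | 2.7% | 2.3% |
| 30% | 29.4% | 19.0% | 10.3% |
| 40% | 66.4% | 52.5% | 13.9% |
| 50% | 91.0% | 83.3% | 7.8% |

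The last column is calculated before rounding.

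**The case against.** The arithmetic is hard to dispute; the case against concerns its weight.

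The limits themselves are stated clearly and are what sites and the committee act on, while the probabilities only describe them. A 9-of-21 limit is an inference, and as written the eighth event suspends the study. If 8 was intended, the error is on the cautious side: the study is more likely to pause at 50% toxicity than claimed, at the cost of 2.3 percentage points more false alarms at 20%. A false alarm brings a pause and a review, not the end of the trial. The response-rate decision rule does not depend on these sentences.

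Most of that stands as a limit on the consequences, and none of it removes the contradiction. The cautious direction is reassuring only if 8 was intended. The disagreement probabilities at 30% and 40% are at toxicity rates for which the plan states no figures, so they illustrate the size and do not contradict a further claim.

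It could also be said that the stated figures are chances of termination, not of reaching a limit. The plan gives no probability of terminating after a pause, so no such figure could have been calculated, and the pair equals a pure crossing probability for 9 of 21. Calling a crossing termination is common shorthand and is a minor wording point here.

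The replacement of patients ("Patients who are not evaluable for response will be replaced") does not explain the figures. With the limit at 8, totals above 21 move further from the stated pair. It bears only on which patients the rule counts.

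**Conclusion.** The stated 2.7% and 83% are wrong for the rule as written. The correct probabilities of reaching either limit are 5.0% and 91.0%: about 1.8 times the stated value at 20% toxicity, and 8 percentage points above it at 50%. The limit and the figures belong to rules that differ by one event at the second limb. The 61% is right and is not part of the error.

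The result assumes independent patients, 21 patients counted, and each discontinuation known when the limit is checked; the stated figures match the same model with a limit of 9. If replacements take the number counted above 21 and the limit stays at 8, the probabilities rise (6.2% at 20% toxicity with 22 patients). The documents do not show whether the limit or the probabilities carry the intended design.

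**What to change.** Reconcile the second limit with its stated probabilities; this review does not say which limit is right. If the figures reflect the intended design, the rule's text has to be brought into line with them. If the written rule stands, replace the sentence giving 2.7% and 83% with:

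> Calculated for 21 patients, the probability that the study is interrupted or suspended under either limb (6 or more of the first 12, or 8 or more of 21) is 5.0% if true toxicity is 20% and 91.0% if it is 50%.

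This wording also makes clear that the figures are chances of a pause, with termination decided afterwards. In the same edit, confirm that the rule counts the same 21 patients the figures assume, since patients not evaluable for response are replaced while everyone dosed stays in the safety analysis.

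The cost is one sentence and one confirmation in section 13.1. If the written rule stands, the stated chance of a pause at 20% toxicity rises from 2.7% to 5.0%; sample size and the response-rate rule are unaffected.
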